Eight participating hospitals will be randomized to a staggered sequence (i.e., steps 1 to 8) of transitioning from UC to STAR group assignments using SAS Enterprise Guide v7.1 (Cary, NC). All eight hospitals will start with a control period of varying length, dependent on timing of transition to the intervention arm. Every four months, one randomly assigned hospital will cross over to initiate the STAR program and remain in the intervention arm through study completion. All patients identified as eligible using the risk model will be allocated to the study ARM that matches the admitting hospital's assignment (STAR or UC). During the intervention phase at each facility (i.e., after transition from UC to STAR), the navigator will receive the list of admitted, high risk patients via secure email.

Study Procedures

Patient identification: Each morning, the list of eligible, high-risk patients is automatically securely transmitted to the study database within REDCap and the study PIs are notified of completed transmission. The list of eligible, high risk patients at hospitals allocated to receive the STAR program (based on randomly assigned months) will also be automatically emailed via secure transmission to the STAR navigators.

Initial contact with the STAR program: After the patient list is generated, the STAR navigator will contact the care team (e.g., bedside nurse, hospitalist) to obtain permission to discuss the STAR program with patients assigned to STAR. At any time, the hospitalist, bedside nurse, or

patient may decline for the patient to participate in the STAR program or any components of usual care.

Summary of STAR services duration: The STAR navigator will provide telephone- and EHR-based support within the hospitalization and to patients across all discharge settings with remote monitoring at specified intervals following hospital discharge. Within 48 hours of discharge, patients allocated to STAR will have their first post-discharge follow-up. They will continue to receive STAR directed services for 90 days following their discharge. Subsequently, they will be transitioned back to the next appropriate care location.

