Irrespective of discharge location (e.g., home versus skilled nursing facility), the STAR navigator will provide monitoring through phone contact with patient, caregiver, or provider (as appropriate for post-acute care location) at <48 hours, 72-96 hours, and 7-10 days post-discharge. These touchpoints will include medication reconciliation, infection and respiratory symptom monitoring, vitals and weight checks, and confirmation that the patient can make scheduled outpatient appointments. Concerns identified through proactive monitoring will prompt a primary care provider contact for follow-up. If the primary care provider cannot be reached after one attempt, the navigator will contact the hospitalist back-up provider. Following the immediate post-acute interval, the STAR navigator will maintain weekly telehealth touchpoints with patients who remain at high-risk for poor outcome (i.e., any previous positive screen, high-risk comorbid condition [e.g., chronic lung disease, heart failure], or low health literacy) and every third week touchpoints with patients considered low-risk after the immediate post-acute interval. These 90-day post-acute touchpoints will include infection and respiratory symptom check, vitals and weight monitoring, and consideration for repeat outpatient provider visit. Identified concerns will prompt attempts to contact the primary care provider followed by hospitalist back-up provider. The STAR support service will complete 90 days post hospital discharge.

Statistical Analysis

Sample Size Determination: This study is designed to detect a 20% relative reduction in composite 90-day mortality and hospital readmission. The usual care group is indicated to have

roughly 40% combined 90-day mortality and readmission rate. With a total sample size of 4392 patients enrolled over 36 unit-months, we will have 90% power ($\alpha=0.05$) to detect a 20% relative reduction in composite 90-day mortality and hospital readmission.

Statistical Methods

Aim 1: Evaluate the effectiveness of an innovative, virtual nurse navigator implementation strategy to improve post-sepsis care.

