All primary and secondary analyses will follow intention to treat approach, such that all patients meeting identical criteria and randomized will be analyzed, regardless of adherence to intervention assignment. This real-world approach will assess intervention effectiveness while limiting selection biases associated with adherence. We will compare the two groups (STAR versus usual care) at baseline for age, sex, race, and comorbidities to assess for balance inferred randomization. The primary outcome is the composite of hospital readmission and mortality at 90 days post hospital discharge. Because hospitals are randomized to STAR in a staggered sequence and the outcome varies at the patient level, we will use a generalized linear mixed-effects model to compare the composite 90-day mortality and readmission primary outcome measure between the intervention conditions, adjusting for clustering effects across multiple levels (e.g., admitting hospital, implementation timing) to include hierarchical data structures. The intervention fixed-effect coefficient will compare STAR versus UC conditions (i.e., UC as reference). We will evaluate covariates for patient (e.g., sex, race, comorbidities, length of stay, discharge disposition [skilled nursing facility, rehabilitation, home]) and organizational factors (e.g., admitting hospital, guideline adherence, urban versus rural setting, implementation timing) to identify any potential differences between study arms. We will include covariates in model if unbalanced between STAR and UC groups. We will also evaluate effect

modification by conducting analyses stratified by these characteristics (e.g., discharge disposition) and by process measures with potential to effect outcomes (e.g., referrals).

Secondary outcomes are described below and will be assessed using the same approach. That is, we will construct generalized linear mixed-effects models, like for the primary outcome analysis, for individual assessments of secondary outcomes and process measures. We will test different distribution parameters to determine the optimal distribution family for each model and outcome variable (e.g., binomial, gamma distributions).

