We do not anticipate substantial missing data because all outcomes are routinely collected variables and utilization is broadly captured within the large integrated system. While utilization may occur outside of CHS, this is not expected to be a major limitation because of CHS market share and accessibility. Specifically, CHS operates three large hospitals in Mecklenburg County, the only acute care hospitals in Anson, Burke, Cleveland, Lincoln, Stanly, and Union counties, where most of this study will be conducted, and more than 40 hospitals in the region overall. Additionally, any utilization that occurs outside the system is anticipated to be non-differentially distributed between groups and thus impact treatment groups equally. Further, internal data indicates nearly 75% of high-risk patients are Medicare-insured and have complete healthcare claims within and outside CHS facilities captured through participation in the ACO managed by CHS. We will leverage this data for subgroup analyses and to explore missing data patterns that can be adjusted using pattern-mixture methods in sensitivity analyses.

All hypothesis tests will be two sided and data will be analyzed using SAS Enterprise Guide v7.1 (Cary, NC) or R v3.5 (Vienna, Austria).

Interim Analysis

Interim analyses will be conducted when 50% of enrollment targets are met and 90-day patient outcomes are obtained. All interim analyses will be presented to the Data and Safety Monitoring Board (a Steering Committee representative, an independent clinician investigator, and an independent biostatistician), who will make a recommendation on continuing the trial as planned or modified. The following analyses will be conducted by the study statistician and provided to the Data and Safety Monitoring Board:

1. Sample size re-estimation

a. Drop-out rate for STAR: We define the drop-out rate for the STAR program to be the rate of nonadherence to the intervention. Non-adherence is defined by those patients who declined, were discharged before contact by STAR staff, and were not able to be contacted after hospital discharge. The population is defined as all patients who were deemed eligible and identified as high risk for readmission or mortality. We propose to assess the drop-out rate in the STAR intervention arm when half of patients have 90-day follow up information available (n=2196). At that time, we will re-estimate the sample size needed for the study using drop-out rates.

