b. Event rate: We propose to re-estimate the sample size based on the combined 90-day hospital readmission and mortality rates for both patients randomly assigned to STAR and usual care when half of the information is available for the trial (n=2196). We will base the re-estimation on the original 20% relative reduction to determine if more patients are needed to maintain 90% power. We will measure the composite outcome as defined for the primary effectiveness analysis, i.e., we will capture all patients with either

date of death or eligible hospital readmission prior to 90 days post discharge as event-positive.

2. Interim efficacy analysis with 50% information (i.e., 50% of target accrual with 90-day follow up data).

We propose to conduct an interim effectiveness analysis of the primary outcome of composite 90-day hospital readmission and mortality rates once 50% of patients have been accrued and have 90-day outcomes. We will use the Haybittle-Peto procedure with boundary of less than 0.001. No additional interim analyses will be planned until the sample size re-estimation and futility analyses are reviewed and a recommendation is made to continue, stop, or modify the study.

3. Futility analysis/conditional power at 50% complete data information (50% of target accrual with 90-day follow-up data). We propose to conduct a futility analysis at 50% information accrual for the trial. The first futility analysis will be conducted at the same time as the sample size re-estimation based on the drop-out rate. Conditional power is the probability of detecting a difference at the end of the study ($p<0.05$) given the current data trend. We will estimate conditional power under the null hypothesis of no difference, the designed alternative of 20% relative reduction, and the current observed trend. A recommendation would be made to stop the study for futility if the conditional power is less than 0.10 for the designed alternative.

**Aim 2: To assess the cost-effectiveness of virtual nurse navigator-driven STAR program
Within-trial Incremental Cost Effectiveness Ratio.**

We will estimate Incremental Cost Effectiveness Ratio (ICER) of STAR versus UC using data derived during the study interval as a measure of benefit to the hospital system. We will estimate ICER as incremental costs divided by incremental QALYs. The intervention group beta weight from cost model will be divided by the intervention group beta weight from QALYs model.

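### With eight randomised hospitals and no small-sample method specified, ordinary mixed-model p-values would not hold the 0.001 interim boundary, and the final 0.05 test would run somewhat high

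*Combined protocol and SAP*

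**What the plan says.** - Randomization: "Eight participating hospitals will be randomized to a staggered sequence (i.e., steps 1 to 8", and "Every four months, one randomly assigned hospital will cross over to initiate the STAR program". The hospital is the only randomised unit.
- Statistical Methods, Aim 1: "we will use a generalized linear mixed-effects model to compare the composite 90-day mortality and readmission primary outcome measure". Hospital and implementation timing are given as examples of clustering levels. The random-effects structure is not fixed.
- End of Aim 1: all tests are two-sided, and "data will be analyzed using SAS Enterprise Guide v7.1 (Cary, NC) or R v3.5 (Vienna, Austria". No procedure or option is named.
- Interim Analysis, item 2: "We will use the Haybittle-Peto procedure with boundary of less than 0.001", applied to the primary outcome at 2196 patients with 90-day data. The item names no separate model, so the Aim 1 model is implied.
- Sample Size Determination and interim item 3 set the final level at 0.05.

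The documents state no ICC, no estimation method, no degrees-of-freedom rule, no small-sample correction and no permutation test. They do not say that uncorrected p-values will be used; they leave this open.

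**The concern.** A Wald z test treats the estimated variance components as known and refers the statistic to a normal distribution. With eight hospitals the between-hospital variance is poorly estimated, and maximum likelihood tends to underestimate it. The standard error of the STAR effect is then too small too often. The relative error is largest far out in the tail, which is where a 0.001 boundary lies. This does not depend on misspecification: it appears when the period effects and random effects are exactly right.

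At stake are the false-positive rate of the recommendation to stop for benefit, the stated 5% level of the final test, and the coverage of confidence intervals from the same model. Sample size re-estimation does not help, because it asks about more patients and not more hospitals.

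**Working it through.** **1. Layout.** "With a total sample size of 4392 patients enrolled over 36 unit-months, we will have 90% power". One crossing every four months for eight hospitals, plus a common control period, gives 9 periods (9 × 4 = 36 months). 4392 / 36 = 122 patients per month, and 4392 / (8 × 9) = 61 per hospital-period with equal hospitals and even accrual. The interim falls at 2196 / 122 = 18 months of enrolment: four full periods (4 × 8 × 61 = 1952) plus half of the fifth (244). Crossings come at months 4, 8, 12 and 16, so four hospitals contribute STAR patients among those 2196.

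**2. The plan's own figure.** The design values are "roughly 40% combined 90-day mortality and readmission rate" and "This study is designed to detect a 20% relative reduction in composite 90-day mortality and hospital readmission", that is 40% against 32%. Individual randomisation would need 755 per arm, 1510 in all, so 4392 must allow for the stepped wedge. The Hussey-Hughes variance is

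Var = Iσ²(σ² + Tτ²) / [(IU − W)σ² + (U² + ITU − TW − IV)τ²],

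with I = 8, T = 9, U = 36, W = V = 204. Hence IU − W = 84, and the second bracket is 1296 + 2592 − 1836 − 1632 = 420. With σ² = 0.36 × 0.64 / 61 = 0.003777 and an assumed ICC of 0.02 (τ² = 0.2304 × 0.02 / 0.98 = 0.004702), SE = 0.02465 and power = Φ(0.08 / 0.02465 − 1.96) = 0.901. For ICC 0.01, 0.03, 0.05 and 0.10, power is 0.915, 0.895, 0.890 and 0.886; at ICC 0 it is 0.988. The stated 90% is reproduced, but over so wide a range of ICCs that it does not reveal which one was used.

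**3. Nominal error.** If p-values were exact, looks at 0.001 and 0.05 with 45 to 50% information would give an overall two-sided alpha of 0.0502 to 0.0503. The boundary itself is not the problem.

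**4. Size under no STAR effect.** Data were simulated with a 40% event rate and fitted with the correct logistic mixed model: fixed periods, STAR, a random hospital intercept and, where stated, a random hospital-by-period effect. Total random-effect variance is (π²/3) × ICC / (1 − ICC); CAC is the cluster autocorrelation, the share of that variance that is constant over time. Fits used penalised quasi-likelihood with ML or REML variance components (12,000 to 24,000 trials each). They were cross-checked with R glmer (Laplace, 2,500 to 6,000 trials). The z tests reject beyond 3.29 (interim) and 1.96 (final).

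| Fit and reference | Assumed ICC | Interim (0.001) | Final (0.05) |
|---|---|---|---|
| ML, hospital intercept, z | 0.01 / 0.02 / 0.05 | 0.0046 / 0.0038 / 0.0022 | 0.069 / 0.059 / 0.053 |
| ML, plus hospital-by-period, z | 0.01–0.05, CAC 0.5–0.9 | 0.0038–0.0078 | 0.065–0.091 |
| glmer, hospital intercept, z | 0.02 | 0.0062 | 0.059 |
| glmer, plus hospital-by-period, z | 0.02, CAC 0.8 | 0.0083 | 0.071 |
| REML, either structure, z | 0.01–0.05 | 0.0017–0.0040 | 0.054–0.062 |
| REML, t with cell-level df | 0.01–0.05 | 0.0003–0.0015 | 0.049–0.057 |
| REML, t with 6 df | 0.01–0.05 | about 0 | 0.017–0.019 |

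Cell-level df are cells minus period, hospital and STAR parameters: 40 − 5 − 7 − 1 = 27 at the interim and 72 − 9 − 7 − 1 = 55 at the end. Monte Carlo standard errors are about 0.0003 to 0.0006 for the interim quasi-likelihood figures, 0.001 to 0.0015 for interim glmer, and 0.002 to 0.005 for the final figures.

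**5. Reading.** Every uncorrected z fit exceeds 0.001 at the interim, by a factor of about 1.7 to 8.3. The final test runs at about 1.06 to 1.8 times nominal. A t reference alone is not enough under ML: at ICC 0.02 and CAC 0.5, t with 27 and 55 df still gave 0.0029 and 0.084. REML with cell-level df came close to nominal at both looks.

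**The case against.** The plan never commits to uncorrected p-values. It permits SAS or R and names no method, and an analyst using REML with a suitable t reference would be near nominal. That is right, and it limits the claim to what happens if nothing is corrected. It does not remove the point: fits that all comply with the text give a final size anywhere from about 0.017 to 0.091, so the error rate of a stopping rule hangs on an unstated option.

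The absolute consequence is also modest. The rates are two-sided; if errors are symmetric, false recommendations for benefit occur in about 0.001 to 0.004 of null trials, against 0.0005 nominal. The Data and Safety Monitoring Board, which includes an independent biostatistician, makes a recommendation; crossing the boundary does not by itself end the trial. At ICC 0.05 with a hospital intercept only, the final excess is 0.3 points. All of this stands and keeps the point below the level of a fatal flaw.

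A reader might infer more than the documents support:
- That the boundary really runs at one narrow value, such as 0.004 to 0.005, with the final test at 0.062 to 0.065. Those values need one ICC, one random-effects structure and an ML Wald test, none of which the plan gives.
- That exactly four hospitals are on STAR at the interim. This holds for the first 2196 patients under even accrual. When their 90-day outcomes are complete, near month 21, a fifth hospital would have crossed at month 20.
- That Kenward-Roger degrees of freedom are shown to solve it. They were not simulated; only t references with cell-level and 6 df were.

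**Conclusion.** The point holds in conditional form. The plan judges a mixed-model test based on eight randomised hospitals against 0.001 and 0.05 and specifies no small-sample method. If ordinary Wald p-values are used, a correctly specified model gives roughly 0.002 to 0.008 at the interim and 0.053 to 0.09 at the end. The direction is consistent across every uncorrected fit examined. The size is not a fact of this plan: it rests on assumed ICCs of 0.01 to 0.05, on whether a hospital-by-period effect exists and is modelled, on ML or REML, and on equal hospital sizes and even accrual. The change should be made before the interim analysis; it does not call the design into question.

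**What to change.** In Statistical Methods, Aim 1, and in interim item 2:

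1. Fix the random-effects structure, including whether a hospital-by-period term is fitted.
2. Fit by a restricted-likelihood type method, and name the procedure and options.
3. Take the interim p-value, the final p-value and the confidence intervals from a small-sample t reference. Check its size by simulation for this design at both looks, over a stated range of ICCs and with realistic hospital sizes. Cell-level df (27 and 55 in the layout above) were close to nominal under REML; 6 df were strongly conservative. Any other choice, Kenward-Roger included, needs the same check.
4. Optionally name a permutation test over the crossing order (8! = 40,320 orders) as the final primary test or as a supporting analysis. If it is primary, say how a disagreement with the model-based interval will be reported. It suits the interim poorly: with four hospitals crossed there are 8 × 7 × 6 × 5 = 1,680 distinct orders, so the smallest attainable p-value is 1 / 1,680, about 0.0006.

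The cost is SAP wording and some computing, plus about 1 to 3 points of power against the uncorrected test. For the permutation test, size was 4.7 to 5.3% and power 0.84 to 0.90, against 0.87 to 0.91 uncorrected. Part of that loss is power the uncorrected test gains by exceeding its level, but power may fall below the planned 90%, and the sponsor should state this.

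### Half of target accrual is defined as 50% information, but in this stepped wedge the information on the STAR effect is half only by coincidence, so conditional power needs a model-based information fraction

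*Combined protocol and SAP*

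**What the plan says.** The Interim Analysis section of the combined protocol and SAP equates accrual with information in three places. Item 1b calls n=2196 half of the information, item 2 explains 50% information as half of target accrual, and item 3 is headed "Futility analysis/conditional power at 50% complete data information (50% of target accrual with 90-day follow-up data").

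Item 3 also gives the definition "Conditional power is the probability of detecting a difference at the end of the study ($p<0.05$) given the current data trend" and the rule: "A recommendation would be made to stop the study for futility if the conditional power is less than 0.10 for the designed alternative". Conditional power is to be reported under the null, the designed alternative and the observed trend. No formula, ICC or other measure of information is given.

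The design is described under Randomization: "Every four months, one randomly assigned hospital will cross over to initiate the STAR program". The Statistical Methods for Aim 1 estimate the STAR coefficient from a generalized linear mixed model that adjusts for admitting hospital and implementation timing.

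**The concern.** In a parallel trial with constant allocation, half of the patients carry close to half of the information, and the label is harmless. Here allocation changes throughout the trial. All hospitals start in usual care, and STAR patients accumulate mainly in the second half. At n=2196 four of the eight hospitals have contributed no STAR patient. How much the interim data say about the STAR coefficient then depends on the ICC, on how correlation decays over time, on hospital volumes and on which hospitals crossed first.

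Conditional power depends directly on the information fraction. If the true fraction is below 0.5 and 0.5 is used, conditional power under the designed alternative is understated and the rule recommends stopping too readily. If the true fraction is above 0.5, the rule is too reluctant. The observed-trend figure given to the board is distorted as well.

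**Working it through.** **Inputs from the documents.** Sample size: "With a total sample size of 4392 patients enrolled over 36 unit-months". Effect: a 20% relative reduction from "roughly 40% combined 90-day mortality and readmission rate", so 0.40 against 0.32. Power is 90% and alpha 0.05; "All hypothesis tests will be two sided". There are eight hospitals and steps of four months. Enrollment runs July 2020 to June 2023, which is 36 months or nine periods, the first all usual care. Hence 4392/(8 × 9) = 61 patients per hospital-period.

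**Assumptions.** A linear approximation to the mixed model, fixed period effects, a hospital random intercept, outcome variance at p = 0.36, even accrual, and an ICC that the documents do not give.

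**Step 1: the plan's 90% power.** An individually randomized comparison of 0.40 with 0.32 needs 755 per arm (1510 in total), so 4392 implies a design effect of 4392/1510 = 2.91. The stepped-wedge generalized least squares calculation gives power of 0.917, 0.906, 0.905 and 0.915 at ICC 0.01, 0.02, 0.05 and 0.10. For example, at ICC 0.02 the final standard error is 0.0244, and 0.08/0.0244 − 1.96 = 1.32, so power is 0.906. The stated 90% is reproduced within 2 points.

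**Step 2: allocation at the look.** n=2196 is reached after 4.5 periods. STAR patients: 61 × (0 + 1 + 2 + 3 + 0.5 × 4) = 488, or 22%. At the end the figure is 2196 of 4392, or 50%.

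**Step 3: information fraction.** t = Var(final)/Var(interim) for the STAR coefficient. At ICC 0.02, t = (0.0244/0.0364)² = 0.45.

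**Step 4: conditional power under the designed alternative.** With positive Z favouring STAR and drift θ = 1.960 + 1.282 = 3.242,

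CP = Φ((Z√t + θ(1 − t) − 1.96)/√(1 − t)).

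Setting CP = 0.10 and t = 0.5 gives Z = (1.960 − 0.906 − 1.621)/0.707 = −0.80. At that Z with t = 0.45, CP = Φ((−0.538 + 1.783 − 1.960)/0.742) = Φ(−0.96) = 0.167.

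Equal hospitals, constant within-hospital correlation:

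| ICC (assumed) | Final power | t | True CP at Z = −0.80 | Z at which true CP is 0.10 | P(stop), no effect, true t |
|---|---|---|---|---|---|
| 0.001 | 0.972 | 0.523 | 0.075 | −0.65 | 26% |
| 0.005 | 0.935 | 0.505 | 0.094 | −0.77 | 22% |
| 0.01 | 0.917 | 0.478 | 0.128 | −0.95 | 17% |
| 0.02 | 0.906 | 0.450 | 0.167 | −1.15 | 12.5% |
| 0.05 | 0.905 | 0.425 | 0.207 | −1.34 | 9% |
| 0.10 | 0.915 | 0.415 | 0.224 | −1.42 | 8% |

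With t = 0.5 the probability of stopping under no effect is Φ(−0.80) = 21%.

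**Step 5: sensitivity.**
- Cluster autocorrelation 0.8, ICC 0.01: power 0.895, t = 0.496, CP 0.10, so almost no error.
- Three hospitals assumed twice the size of the other five: at ICC 0.10 the 95th percentile of CP over crossover orders is 0.34.
- Three hospitals assumed three times the size: the 95th percentile is already about 0.34 at ICC 0.02, and the worst order at ICC 0.10 gives 0.44. In the other direction, the 5th percentile at ICC 0.01 is about 0.05.
- Without period adjustment t would be 0.25 to 0.35, but power would then be 0.998 or more, which does not match the stated 90%.

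**Step 6: consequence for the trial.** If the designed 20% reduction is true, P(Z < −0.80) = Φ(−0.80 − 3.242√t), which is 0.10% at t = 0.50, 0.15% at t = 0.45 and 0.30% at t = 0.36. Power lost is below 0.1 percentage point.

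**Step 7: observed-trend figure.** CP = Φ((Z/√t − 1.96)/√(1 − t)). At Z = 1.0 this is 0.22 for t = 0.50, 0.26 for t = 0.45 and 0.31 for t = 0.40.

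**The case against.** The strongest reply is that the plan does not say 0.5 enters any formula. The parenthesis can be read as fixing when the look happens. A statistician who takes the interim standard error from the planned mixed model and projects the final variance would comply with the plan and make no error. This stands: the documents show a mis-stated information measure, not a miscalculation. But the text states the equivalence three times and offers no other measure, so using 0.5 would comply equally well.

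Second, a reader might infer that the rule is biased towards stopping, with a true conditional power as high as one third at the threshold. The documents do not support that as a general statement. They give no ICC and no hospital volumes. Equal hospitals give at most 0.22 over ICC 0.01 to 0.10, and higher values need assumed unequal sizes and an unfavourable order. The remark on large and sole-county hospitals in the missing-data text concerns data capture; it does not list the eight sites or their volumes. At low ICC the error reverses.

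Third, a reader might fear that an effective programme would be stopped. The threshold lies where the estimate favours usual care, so that risk is about 0.1 to 0.3% for t between 0.50 and 0.36. Stopping more often under no effect is not in itself a harm, since that is what a futility rule is for. The rule is also advisory, and the board includes an independent biostatistician and sees conditional power under three scenarios. All of this stands and limits the weight of the point. What remains is that the board's figures may not mean what they say.

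**Conclusion.** The point holds as one of definition. Half of accrual is not half of the information on the STAR coefficient except by coincidence.

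- **Settings closest to the stated 90% power** (equal hospitals, constant correlation, ICC 0.01 to 0.10): t is about 0.42 to 0.48. If 0.5 were used, the 0.10 threshold would mean a true conditional power of about 0.13 to 0.22. One setting that also fits (ICC 0.01, autocorrelation 0.8) shows almost no error.
- **Reverse direction:** at very low ICC, or with some hospital sizes and orders, t exceeds 0.5 and the threshold means about 0.04 to 0.09.
- **Unequal hospitals:** with some hospitals assumed 2 to 3 times the size of the others and an unfavourable order, about 0.34 can be reached, and more in the most extreme orders.

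The effect on overall power is negligible. What changes is the conditional-power figures given to the board and the stopping frequency under no effect: 21% with t = 0.5, against about 8 to 17% with the true fraction at ICC 0.01 to 0.10. All of these figures rest on an assumed ICC and a linear approximation. The case for a change rests on its low cost, not on a threat to the trial.

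**What to change.** In Interim Analysis items 1b, 2 and 3, keep the look at n=2196 with 90-day data and keep the 0.10 threshold, but delete the statement that this is half of the information. Add wording such as: the information fraction in every conditional-power calculation is the projected final variance of the STAR coefficient divided by its interim variance, both from the planned mixed model; the final variance is projected from the remaining steps and the interim variance components; the report to the board gives the fraction, the STAR and usual care counts, and the number of hospitals that have crossed.

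This is correct whether the fraction proves to be above or below 0.5, so the ICC need not be settled first. The date of the look, the efficacy boundary and the planned sample size are untouched.

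The cost is a short extra calculation by the study statistician. Its weakness is that variance components estimated at the interim from eight hospitals are imprecise, so the fraction should be shown over a small range of values.
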